3.5 Concomitant Medication

Patients are allowed to continue the medications that they are taking at baseline. Patients may also receive concomitant medications that are medically indicated as standard care for the treatment of symptoms and intercurrent illnesses. Section 8.13 of the protocol details prohibited concomitant medications.

3.6 Study Analysis Populations

The following analysis populations are defined:

3.6.1 Full Analysis Set (FAS)

The Full analysis set (FAS) will include all patients who receive at least one dose of MOR00208 and/or one dose of idelalisib in Cohort A and/or one dose of 100 mg daily dose of venetoclax in Cohort B. The FAS will be the primary analysis population for the secondary endpoint Overall Response Rate (ORR).

In the FAS patients will be analyzed according to the cohort they were enrolled (intent-to-treat principle).

3.6.2 Per Protocol Set (PPS)

The Per Protocol Set (PPS) consists of all patients in the FAS who did not have any protocol deviations that could confound the interpretation of the efficacy analyses conducted on the FAS. Patients with no post-baseline assessment of response will be excluded from the PPS. The PPS will be used for a sensitivity analysis of the secondary endpoint overall response rate (ORR).

Decisions about whether a protocol deviation is relevant for the exclusion of a patient from the PPS will be made before database closure. In the PPS patients will be analyzed according to the cohort they were enrolled.

3.6.3 Safety Analysis Set (SAF)

The Safety Analysis Set (SAF) includes all patients who received at least one dose of any study treatment and had at least one post-baseline safety evaluation. A record of death or “no adverse event” constitutes a valid safety assessment. Data for patients with no post-baseline safety assessment will only be listed in the FAS. Patients will be analyzed according to the study treatment they actually received. The SAF will be used for the primary endpoint analysis, i.e., incidence and severity of adverse events.

3.6.4 PK Analysis Set (PKAS)

The PK analysis set (PKAS) will include all patients who received at least one dose of study medication MOR00208 and have at least one quantifiable serum MOR00208 concentration. PK parameters will be calculated as data permit.

3.6.5 Immunogenicity Analysis Set (IAS)

The Immunogenicity Analysis Set (IAS) will include all patients who have at least one anti-MOR00208 antibody assessment.

3.6.6 Other Populations Defined for Tables and Listings

Two further populations are defined for the case any additional tables and listings will be presented:

- All patients
- All enrolled patients
- Screening failure patients

The “all patients” population consists of all patients who have signed informed consent. The ‘all enrolled patients’ population includes all patients who received at least one dose of any study treatment.

The following **Table 3** summarizes the analyses being performed for each analysis set.

Table 3: Overview of the Analyses Performed on the Different Study Populations

Analysis	All patients	FAS	PPS	SAF	PKAS	IAS
Patient disposition	x	x				
Summary of demographic and baseline characteristics		x		x		
Incidence, frequency and severity of adverse events				x		
Summary of vital signs, 12-lead ECG, laboratory safety evaluations				x		
ECOG and B-symptoms				x		
Overall response rate		x	x			
Study treatment (exposure, compliance, dose reductions, dose interruptions)		x		x		
Summary of prior CLL therapies		x		x		
Summary of pre-medication, prior medication, concomitant medication, and medical history/current medical conditions		x		x		
Pharmacokinetic analyses					x	
Immunogenicity analyses						x
Descriptive biomarker analyses		x				

3.7 Withdrawn Patients

Once a patient is withdrawn from the study, the patient may not re-enter the study.

3.8 Randomization

The study is a non-randomized trial.

3.9 Blinding

This is an open label study.

3.10 Sample Size

The primary endpoint of this study is the incidence and severity of AEs in Cohort A (MOR00208 combined with idelalisib) and Cohort B (MOR00208 combined with venetoclax) and will be analyzed

descriptively. In each cohort approximately 12 patients will be enrolled. No formal sample size calculation was performed and no formal statistical hypothesis testing is planned.

4 Statistical Methodology

4.1 General Statistical Approaches

4.1.1 Descriptive Statistics

All data will be summarized using appropriate statistics (counts/percentages for discrete variables, mean, median, standard deviation, minimum, maximum, number of valid observations for continuous variables) for tabulation purposes. For specific variables, 95% confidence limits of means will be presented. The number and percentage of patients in each category will be presented for categorical variables. For categorical variables, the number and percentage of patients with missing data will be provided. Data from all sites will be pooled for all analyses.

4.1.2 Statistical Significance

No formal statistical hypothesis testing is planned.

4.1.3 Subgroup Analyses

No subgroup analyses are planned in the study.

4.1.4 Visit Window

Analysis Window

For parameters that will be summarized by visit, the nominal visit as recorded on the eCRF will be used. There will be no additional analysis windowing done based on the assessment date.

Unscheduled visits prior to C1D1 will be included for the calculation of baseline values.

Unscheduled scans will be used for determination of tumor response efficacy endpoints.

Selection of Data in the Event of Multiple Records in a Window

Depending on the statistical analysis method, single values may be required for each analysis window. For example, change from baseline by visit usually requires a single value per visit, whereas a time-to-event analysis would not require 1 value per analysis window but rather 1 value for the study. Unless otherwise noted throughout the rest of this document, when a single value is needed, the following rule(s) will be used:

- If more than 1 assessment occurs during the same nominal visit, select the record closest to the nominal day for that visit.
- If there are 2 assessments that are equidistant from the nominal day, the data of the assessment after the scheduled study day will be used.
- The last measurement will be used if multiple measurements are all taken on the same day.

4.1.5 Exclusion of Data from the Statistical Analysis

No data will be excluded from the analyses, including any outliers.

4.1.6 Listings

All data collected in the CRF will be presented in the listings.

4.2 Types of Planned Analysis

4.2.1 Primary Analysis

The primary analysis of each cohort to evaluate safety and preliminary efficacy will be based on the safety data and response assessment of the enrolled patients up to the time point of 3-18 months after last patient started treatment in Cohort B.

4.2.2 Final Analysis

The final analysis will be conducted at the end of the study defined as 5 years after the first patient was enrolled (C1D1) or approximately 30 days after last patient received his last treatment, whichever comes first.

4.3 Disposition of Patients

The number of patients screened, the number (%) of screen failures and the number of patients with each reason for screen failure will be presented (by cohort). All patients will be included.

The following summaries will be provided by cohort based on the total number of enrolled patients:

- An overview table will be provided by cohort and will include the number of patients enrolled, the number (%) of patients in each analysis set (FAS, PPS, SAF, PKAS and IAS).
- Number (%) of patients who were treated with study drug (split by MOR00208, idelalisib/venetoclax, and treated with both drugs).
- Number (%) of patients who were enrolled but not treated with study drug (split by MOR00208 and idelalisib/venetoclax).
- Number (%) of patients who discontinued treatment including the reason for discontinuation.
- Number (%) of patients who are still on any treatment (only for the primary analysis). The median time on study will be reported for patients in the FAS, which is defined as follows: $[(\text{Date of Death/last Visit including the End of Treatment Visit}) - (\text{Date of first dosing with any study drug}) + 1] / 30.4375$.

The median time on study will be derived using Kaplan-Meier-Methodology. Patients still on study at data cut-off will be censored.

The individual time on study will be graphically illustrated by a 'Swimmers Plot'. The graph will indicate the point in time the best response is reached, the best response (complete response vs. partial response), the number of prior treatment lines, and the reason for BTK inhibitor discontinuation in the last BTK inhibitor containing line. Moreover, the point in time MRD negativity is reached will be shown (see Section 4.9.3). For MRD negativity it will be differentiated between blood and bone marrow assessments, i.e., it will be indicated in the 'Swimmers Plot' when MRD negativity is reached as assessed in blood vs. bone marrow.

4.4 Baseline and Demographic Characteristics

4.4.1 Demography/Baseline Characteristics

All summaries will be presented overall and by cohort in the FAS and SAF. For categorical variables, the number and percentage of patients with missing data will be provided. Demographic and baseline characteristics will include the following:

- age (both continuous and categorical, i.e., <65 and ≥ 65 , <70 and ≥ 70)
- sex and race
- height and weight
- ECOG and disease staging (see section 4.4.2)

- number of prior systemic treatment lines
- time since first CLL/SLL diagnosis (i.e., the interval between the date of first CLL/SLL diagnosis and the screening visit; reported in months)
- time on BTK inhibitor treatment (months) in the most recent prior therapy line containing a BTK inhibitor (not necessarily the last line before entering COSMOS). The following terms will be considered to find the last BTK-containing therapy line: ‘ibrutinib’, ‘imbruvica’, ‘ACP-196’, ‘acalabrutinib’, ‘CC-292’, ‘AVL-292’, ‘ONO-40-59’, ‘BGB-3111’. The variable will be derived as follows: [(End of treatment date for the BTK inhibitor) – (Treatment start date for the BTK inhibitor) + 1]/30.4375.
- the number of patients with beta-2 microglobulin levels >3mg/L at baseline (3 mg/L corresponds to 254.45 nmol/L).
- the number of patients with:
 - neutrophil count $\leq 1.5 \times 10^9$ cells/L at baseline
 - hemoglobin ≤ 11 g/dL at baseline
 - platelet count $\leq 100 \times 10^9$ platelets/L at baseline

The last three items will be summarized for the FAS only. For the time on BTK inhibitor treatment in the most recent prior therapy line containing a BTK inhibitor the following imputations for missing start and stop dates will be made: If the day of the start or stop date is missing but the month is present the day will be imputed by the 15th of the month. If the month of the start or stop date is missing no imputations will be done and the time on BTK inhibitor will be considered as missing.

The demography and baseline characteristics assessed will also be listed by patient.

Note:

- Weight recorded at all the cycles will be presented in the summary of vital signs;
- Baseline BMI will be calculated as: weight at baseline (kg)/squared height at Cycle 1 Day 1 (m^2).

4.4.2 Disease Staging

The “Binet staging system” and “Modified Rai Clinical Stage” for disease staging information collected at baseline will be summarized by cohort.

The Binet clinical staging system and the modified Rai clinical staging system for CLL/SLL comprise three stages (see Section 6.1).

4.4.3 FcγRII/III Gene Mucosal Cheek Swab

Following subgroups will be defined: FcγRIIIa high affinity (FCGR3A-158V homozygosity) vs. FcγRIIIa low affinity (FCGR3A-158F homozygosity, or FCGR3A-158F/V heterozygosity). FcγRIIa high affinity (FCGR2A-131H homozygosity) vs. FcγRIIa low affinity (FCGR2A-131R homozygosity, or FCGR2A-131H/R heterozygosity). The number (%) of patients in each subgroup will be summarized by cohort.

4.4.4 Cytogenetic Risk

Listings and tables for the mutational status of genes such as immunoglobulin heavy-chain variable gene (IGHV), NOTCH1, tumor protein p53 (TP53), BTK, phospholipase C $\gamma 2$ (PLC $\gamma 2$) will be presented. The tables will summarize the number and proportion of patients with mutations present in the aforementioned genes.

Similarly, information will be provided for both translocations and deletions associated with prognosis. Genetic lesions or translocations will be determined by *fluorescence in situ hybridization*

(FISH). The number and proportion of patients with abnormal FISH results for the genetic regions 17p13, 11q13, 13q14, 13q34, 14q32, 6q22-q23 will be presented. The number (%) of patients with complex karyotype will be summarized.

Listings will display detailed information on test results for each individual patient.

4.5 Medical History and Current Medical Conditions

Medical History and Current Medical Conditions will be summarized by body system and by toxicity grade for each treatment group. Summaries will be produced using the SAF and FAS.

Notes:

- Toxicity grade will be coded according to National Cancer Institute (NCI) Common Terminology Criteria for Adverse Events (CTCAE) V4.03 or higher.
- Medical history is defined as records in the “Medical History and Current Medical Conditions”- eCRF form which are not ongoing at Cycle 1 Day 1.
- Current medical conditions are defined as records in the “Medical History and Current Medical Conditions”- eCRF form which are ongoing at Cycle 1 Day 1.

4.6 Prior and Concomitant Medications and Therapies

Prior medications and concomitant medications will be summarized by cohort for the SAF and FAS using frequency distributions and percentages by Therapeutic Subgroup (2nd level of the Anatomical Therapeutic Chemical [ATC] classification) and Preferred Name.

The medications will be classified according to the following rules:

- Prior medication: start date < date of start of treatment period and stop date ≤ date of start of treatment period
- Concomitant medication: date of start of treatment period ≤ start date < date of study completion/discontinuation
- Prior and Concomitant Medication: start date < date of start of treatment period and stop date > date of start of treatment period or ongoing

The prior and concomitant medications will be listed by Therapeutic Subgroup (2nd level of the ATC classification) and Preferred Name for each patient.

CLL/SLL-specific prior therapies:

The best response and duration of response to the previous regimens patients received will be listed. Duration of Response (DoR) to previous regimens is defined as time (in months) from date of assessment of initial tumor response (CR or PR/PRL) to date of assessment of tumor progression (PD). A partial completion date of initial response and progression will be handled using the algorithm specified in section 4.14.1 (handling of missing data). Furthermore, the time since the completion of last regimen will be listed. Partial completion dates will be imputed using the algorithm specified in section 4.14.1 (handling of missing data).

The number (%) of patients who received 1, 2, 3, etc. prior regimens will be provided. Descriptive statistics will also be provided for the last regimen patients received prior to study entry and the best response (n, %) and duration of response to last therapy (in months). The reason for discontinuation of prior BTK inhibitor will be listed and summarized. The following terms will be used to identify prior BTK inhibitor therapy:

- ibrutinib and imbruvica
- acalabrutinib and ACP-196
- CC-292 and AVL-292

- ONO-40-59
- BGB-3111

Additionally, listings on CLL/SLL-specific surgeries, radiation, and stem cell transplantations will be presented. The number and proportion of patients who have experienced these procedures will be tabulated.

4.7 Study Treatment

All analyses on study treatment will be conducted on the SAF and the FAS.

4.7.1 Duration of Exposure

Exposure to combination treatment (i.e., both MOR00208 and idelalisib or venetoclax) and each individual study drug will be summarized for the FAS and the SAF.

4.7.1.1 Duration of Exposure to Each Individual Study Drug

Duration of exposure to an individual study drug (days) = (last date of exposure to study drug) – (date of first administration of study drug) + 1.

Taking into account the period of rest between infusions, the **last date of exposure** is defined as follows:

- For MOR00208: When the study drug is administered over several regular doses with regular time intervals, the last date of exposure is identified according to the planned dose schedule of the cycle. If no rest period is included in the cycle then the last date of exposure is: (last date of administration of the study drug) + (length of time interval-1). **Length of time interval:** 7 days in Cycle 1-3 and 14 days in Cycle 4-6 a, and 28 days from Cycle 7 onwards.
- For idelalisib and venetoclax, the last date of exposure will be defined as the last date of administration.
- For idelalisib and venetoclax, temporary dose interruptions will not be considered for calculation.

4.7.1.2 Duration of Exposure to Combination Treatment (i.e., the combination of *both* MOR00208 and idelalisib/venetoclax at the same time)

Duration of exposure to combination treatment (days) = (last date of exposure to both MOR00208 and idelalisib/venetoclax) – (date of first administration of study treatment) + 1.

The last date of exposure for each individual drug is specified in *Section 4.7.1.1*.

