In Cohort A there will be two safety evaluations. After completion of the first cycle (4 weeks) the safety data of the first three patients will be evaluated. This evaluation will be done by an Independent Data Monitoring Committee (IDMC) composed of experts in the field of oncology and clinical biostatistics who have no other role in the study and do not have an affiliation with the Investigators or the sponsor. After the evaluation of the safety data from the first 3 patients for Cycle 1 of treatment and a positive recommendation from the IDMC the next 7- approximately 9 patients may be dosed in parallel. An additional IDMC review will take place after 10 patients completed at least 1 cycle of treatment.

In Cohort B the safety evaluation will be performed by the IDMC after the first 10 patients completed at least 5 weeks of combination treatment. The evaluation will be done by the IDMC as already described. Importantly, all patients in Cohort B, who participate in the safety run-in phase, will be hospitalized on the day of the first two dose escalations of venetoclax (C1D8 and C1D15).

The criteria for the evaluation of safety of the combination therapy will be defined by the IDMC and laid down in the Safety Management Plan of the trial.

During the study, MOR00208 will be administered as infusions 12.0 mg/kg in 28-day cycles. From Cycle 1 to 3, each cycle will consist of weekly infusions (on Day 1, Day 8, Day 15 and Day 22). In Cycle 1, an additional loading dose will be administered on Day 4. From Cycle 4 to 6, MOR00208 will be administered on a biweekly basis with infusions on Day 1 and Day 15 of each cycle. Thereafter, MOR00208 will be administered on Day 1 of each cycle starting with Cycle 7 Day 1.

Idelalisib will be self-administered twice daily starting on Day 1 of each cycle. Venetoclax will be self-administered (except during hospitalization) starting from Cycle 1 Day 8 and on Day 1 of each cycle onwards. Treatment with idelalisib or venetoclax may be modified in a de-escalating fashion or discontinued based upon clinical and laboratory findings. In case idelalisib or venetoclax treatment was stopped due to side effects suspected to be related to idelalisib or venetoclax, the patient may continue MOR00208 treatment.

Progressive disease will require discontinuation of study medication.

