3.3.2 Treatment administration

MOR00208

MOR00208 will be administered IV at a dose of 12.0 mg/kg.

For the first 3 months (3 cycles) of the study, each cycle will consist of a MOR00208 infusion on Day 1, Day 8, Day 15 and Day 22 of the cycle. In addition, a loading dose will be administered on Day 4 of Cycle 1. Thereafter, MOR00208 will be administered on a biweekly basis (every 14 days) with infusions on Days 1 and 15 of each 28-day cycle from Cycle 4 to 6, and on a monthly basis on Day 1 of each cycle from Cycle 7 Day 1.

Idelalisib

The recommended starting dose for idelalisib is 150 mg orally, twice daily (BID). It may be taken with or without food approximately at the same time of the day. Ideally, doses should be taken at ~12-hour intervals (e.g., at ~8 AM and at ~8 PM) on a BID schedule beginning ~30 minutes prior to the initial MOR00208 infusion.

Patients will self-administer the dose of 150 mg twice daily orally continuously during the study duration. Treatment may be continued up to 24 cycles, or until progression of disease, withdrawal of consent, unacceptable toxicity, death or patient is lost to follow-up, whichever occurs first.

Venetoclax

[figure not shown]
Venetoclax dose should be administered according to a weekly ramp-up schedule over 5 weeks to the recommended daily dose of 400 mg.

Figure 2 illustrates this initial ramp-up. The dosing schedule for ramp-up phase is given as follows, daily dose of venetoclax: 20 mg 1st week of combination treatment, 50 mg 2nd week, 100 mg 3rd week, 200 mg 4th week and 400 mg 5th week and thereafter. The 5-week ramp-up dosing schedule, starting on C1D8, is designed to gradually reduce tumor burden (debulk) and decrease the risk of TLS. Assessment of patient-specific factors for level of risk of TLS and prophylaxis for TLS should be performed prior to first dose of venetoclax (see Section 8.10.1 of the protocol).

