 - **For Cycles with two or more eCRF log lines (two log lines in case of one dose change, or treatment interruption with re-initiation in the same Cycle):**
E.g., for two log lines:
(Actual Total Daily Dose as entered in the eCRF [mg] in log line 1 x Number of days on treatment in log line 1) + (Actual Total Daily Dose as entered in the eCRF [mg] in log line 2) x (Number of days on treatment in log line 2).

Note: Actual Total Daily Dose may be identical for different log lines (in case of interruption), or different in case of dose change.

- The total dose ***used*** per Cycle can be derived as follows:
 - **For Cycles with one eCRF log line:**
(Actual Total Daily Dose as entered in the eCRF [mg] / 2) x (Number of tablets dispensed – Number of tablets returned).
 - **For Cycles with two or more eCRF log lines:**
 - ❖ **All log lines contain information on the number of tablets dispensed, and number of tablets returned (in case of dose change):**
E.g., for two log lines:
[(Actual Total Daily Dose as entered in the eCRF [mg] in log line 1 / 2) x (Number of tablets dispensed in log line 1 – Number of tablets returned in log line 1)] + [(Actual Total Daily Dose as entered in the eCRF [mg] in log line 2 / 2) x (Number of tablets dispensed in log line 2 – Number of tablets returned in log line 2)].
 - ❖ **All log lines for a particular Cycle contain the information on the number of tablets dispensed, and only the last log line for a particular Cycle contains number of tablets returned (in case of treatment interruption and re-initiation of treatment in the same Cycle):**
E.g., for two log lines:
[(Actual Total Daily Dose as entered in the eCRF [mg] in log line 1 / 2) x (Number of tablets dispensed in log line 1)] - [(Actual Total Daily Dose as entered in the eCRF [mg] in log line 2 / 2) x (Number of tablets returned in log line 2)].

- Calculation of compliance for a particular Cycle (%):

(sum of total dose *used* for all log lines pertaining to a particular Cycle) / (sum of total *planned* dose for all log lines pertaining to a particular Cycle) * 100.

Venetoclax

The planned daily doses of venetoclax in the ramp-up phase and beyond are as follows:

- 20 mg 1st week (study days 8 to 14)
- 50 mg 2nd week (study days 15 to 21)
- 100 mg 3rd week (study days 22 to 28)
- 200 mg 4th week (study days 29 to 35)
- 400 mg 5th week and thereafter (study days 36 and above)

Different tablet strengths are being used to target a particular Actual Total Daily Dose:

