4.10.1.1 Treatment-emergent adverse events (TEAEs)

An **on-treatment adverse event (or Treatment-emergent Adverse Event – TEAE)** is defined as:

- An adverse event that occurred in the following time interval (including the lower and upper limits):
 - date of first administration of study treatment
 - until 30 days after last study drug administration
- An adverse event present prior to the study treatment start but increased in severity after treatment start.
- An adverse event occurring or worsening later than 30 days after the last treatment if suspected to be related to the study drug.

If the last date of study drug administration is missing, on-treatment assessments/events include any assessment/event recorded in the database and which occur after the start date of study treatment. Safety summary tables including summaries of on-treatment deaths will be based only on on-treatment assessments/events.

An AE present prior to the study treatment start but increased in severity after treatment start, will also be included as TEAE.

The handling of partially or completely missing AE start and end dates/times in the determination of the status of the AE is described in detail in Section 4.14.1.

The incidence of treatment-emergent AEs will be summarized in incidence tables. If a patient experiences more than one occurrence of the same AE, the occurrence with the highest toxicity grade/greatest severity and the closest association with the study drug will be counted in the summary tables. All AEs will be listed by patient, along with information regarding onset, duration, relationship to study drug, intensity, toxicity grade, action taken with study drug, treatment of event, and outcomes.

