4.10.1.7 AE summaries

4.10.1.7.1 TEAEs (serious and non-serious)

The following summaries will be provided:

- i. All TEAEs regardless of study treatment relationship by primary SOC, PT and grade.
- ii. All TEAEs regardless of study treatment relationship by primary SOC, PT and intensity.
- iii. Most frequent TEAEs (*at least in 10% of the patients*) regardless of study treatment relationship by SOC, PT and grade.
- iv. TEAEs regardless of study treatment relationship \geq grade 3 by primary SOC, PT and grade.
- v. TEAEs regardless of study treatment relationship of grade 3 or grade 4 by primary SOC, PT and grade.

- vi. TEAEs regardless of study treatment relationship starting in Cycle 1 (reported for Cohort A only).
- vii. TEAEs regardless of study treatment relationship starting before Cycle 2 Day 15 (reported for Cohort B only).
- viii. TEAEs suspected to be related to the study drug by primary SOC, PT and grade (split by MOR00208, idelalisib/venetoclax, both MOR00208 *and* idelalisib/venetoclax, or any study drug).
- ix. TEAEs suspected to be related to the study drug by primary SOC, PT, and intensity (split by MOR00208, idelalisib/venetoclax, both MOR00208 *and* idelalisib/venetoclax, or any study drug).
- x. TEAEs suspected to be related to the study drug of \geq grade 3 by primary SOC, PT and grade (split by MOR00208, idelalisib/venetoclax, both MOR00208 *and* idelalisib/venetoclax, or any study drug).
- xi. TEAEs suspected to be related to the study drug of grade 3 or grade 4 by primary SOC, PT and grade (split by MOR00208, idelalisib/venetoclax, both MOR00208 *and* idelalisib/venetoclax, or any study drug).
- xii. Most frequent TEAEs suspected to be related to the study drug (*at least in 10% of the patients*) by primary SOC, PT and grade (split by MOR00208, idelalisib/venetoclax, both MOR00208 *and* idelalisib/venetoclax, or any study drug).
- xiii. TEAEs leading to any action on MOR00208, on idelalisib/venetoclax, on both MOR00208 *and* idelalisib/venetoclax, or any study drug regardless of study treatment relationship by primary SOC, PT and grade.
Note: Any Action = Dose reduction/Dose interruption/Permanent discontinuation.
- xiv. TEAEs leading to discontinuation of treatment (split by MOR00208, idelalisib/venetoclax, both MOR00208 *and* idelalisib/venetoclax, or any study drug) regardless of study treatment relationship by primary SOC, PT and grade.

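### SAP 4.7.1.2 starts the combination-exposure clock at the first dose of any study drug, so Cohort B combination exposure is overstated by about 7 days in the descriptive exposure tables.

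*SAP*

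**What the plan says.** The heading of SAP 4.7.1.2 describes the variable as exposure to "MOR00208 and idelalisib/venetoclax at the same time". The formula takes the last day on which the patient counts as exposed to both drugs and subtracts the "date of first administration of study treatment) + 1". The end of the interval is therefore tied to both drugs. The start is tied to study treatment, a term that the SAP does not define.

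Elsewhere the term covers a single drug. The safety set (SAP 3.6.3) needs "at least one dose of any study treatment". The treatment-emergent window (SAP 4.10.1.1) opens on the "date of first administration of study treatment", and SAP 4.10.1.6.2 flags an event as pre-treatment only if it began before any study drug was given.

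In Cohort B the drugs do not start together. MOR00208 starts on Cycle 1 Day 1, and the venetoclax schedule in SAP 4.7.4 begins with "20 mg 1st week (study days 8 to 14". SAP 3.3.2 counts combination weeks from that point: "20 mg 1st week of combination treatment, 50 mg 2nd week, 100 mg 3rd week".

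SAP 4.7.1.3 reports exposure in weeks, in categories (1-2], (2-4], (4-6] and so on. The results go into Tables 14.3.7.5.1 (FAS) and 14.3.7.5.2 (SAF).

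**The concern.** The formula does not measure what its heading describes. In Cohort B the first week is MOR00208 alone by design, yet the formula counts it as combination exposure. In Cohort A both drugs start on Day 1, so the same table would measure the two cohorts differently.

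The primary objective is the safety of the combinations, and time on both drugs is part of the context for reading the adverse event tables. The excess is nearly constant in days. It therefore weighs most on patients who stop early, and it can move a patient into a higher exposure category in a cohort of about 12.

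**Working it through.** The plan states no exposure figure to reproduce, so the check is date arithmetic. Study days are numbered with Cycle 1 Day 1 as day 1.

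**Inputs**
- First MOR00208 dose: day 1 (SAP 3.2).
- First venetoclax dose: day 8 (SAP 4.7.4), visit window ±1 day (SAP Table 2).
- First idelalisib dose: day 1, about 30 minutes before the first infusion (SAP 3.3.2).
- Last MOR00208 exposure day: last infusion + interval − 1, with intervals of 7, 14 and 28 days for Cycles 1-3, 4-6 and 7 onwards (SAP 4.7.1.1).
- Last oral-drug exposure day: last day taken (SAP 4.7.1.1).

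**Formulas.** Let M and V be the last exposure days for MOR00208 and venetoclax, and s the first venetoclax day.
- As written: min(M, V) − 1 + 1.
- Overlap: min(M, V) − s + 1.
- Excess: s − 1, which is 7 days for s = 8 and 6 or 8 days for s = 7 or 9. In Cohort A the second drug also starts on day 1, so the excess is 0.

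**Worked example (28 days on both drugs; the 28 days is an illustration).** The last infusion is on day 29, so M = 29 + 6 = 35. The last venetoclax day is V = 35.
- As written: 35 − 1 + 1 = 35 days = 5.0 weeks, category (4-6].
- Overlap: 35 − 8 + 1 = 28 days = 4.0 weeks, category (2-4].

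**Other durations, s = 8**

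| Days on both drugs | Reported days | Weeks, overlap v reported | Excess |
|---|---|---|---|
| 28 | 35 | 4.0 v 5.0 | 25% |
| 35 | 42 | 5.0 v 6.0 | 20% |
| 84 | 91 | 12.0 v 13.0 | 8.3% |
| 665 | 672 | 95.0 v 96.0 | 1.1% |

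The last row is the full 24 cycles: Cycle 24 Day 1 is day 23 × 28 + 1 = 645, and 645 + 27 = 672.

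**Check against the SAP's own count.** The Cohort B review takes place "after the first 10 patients completed at least 5 weeks of combination treatment". The matching adverse event summary is "TEAEs regardless of study treatment relationship starting before Cycle 2 Day 15 (reported for Cohort B only"). Cycle 2 Day 15 is day 28 + 15 = 43, so the summary runs through day 42. Days 8 to 42 are 42 − 8 + 1 = 35 days, exactly 5 weeks. The 4.7.1.2 formula gives 42 days, or 6.0 weeks, to the same date.

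**Categories.** A single MOR00208 infusion on day 1 counts as exposure to day 1 + 6 = 7, that is 7 days or 1.0 week. The interval (1-2] excludes 1.0, and no lower category exists. The two-week steps suggest that (0-2] was meant.

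**The case against.** The strongest reply is that study treatment is undefined. SAP 4.7.1.1 says study drug for single agents and 4.7.1.2 changes the term, under a heading limited to both drugs. Protocol 8.1 also describes the treatment as consisting of MOR00208 with its partner. A programmer could therefore start the clock correctly at first combined dosing. This stands in part: the fault lies in the wording, and the 7 days follow only on the literal reading. That reading is still the better supported. If the same phrase meant the combination in 4.10.1.1, events in the MOR00208-only week would fall outside the window that opens at treatment start, although 4.10.1.6.2 would not call them pre-treatment.

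It is also true that each drug's exposure is summarised separately and that the Day 8 start is stated plainly, so a careful reader could work out the lag. That limits the harm but does not correct the combination row.

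A reader might infer more than the documents support:
- **That the IDMC review comes a week early.** The review is set by completed weeks of combination treatment, which SAP 3.3.2 counts from the first venetoclax week. Nothing links it to 4.7.1.2.
- **That adverse event rates are diluted.** The SAP reports event counts and percentages of patients, not rates per exposure time.
- **That one-drug patients are left without a rule.** They have no last day on both drugs, so the value is missing. SAP 4.14.1 shows missing values in their own category and leaves them out of summary statistics for continuous data. SAP 2 also adds columns by treatment actually received.
- **That the combination row always exceeds the venetoclax row.** It does so only if M is at least V − 6; otherwise the excess over true overlap remains but is not visible in that comparison.
- **That interrupted oral-drug cycles are wrongly counted as completed.** Days inside an interruption with restart in the same cycle do leave the compliance denominator. But 4.7.4 measures adherence to the assigned dosage, 4.7.3 tabulates interruptions and their reasons, and MOR00208 doses skipped for toxicity are likewise left out of compliance. This is a choice of definition, not an error.

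**Conclusion.** The point holds as a minor one. Read literally, SAP 4.7.1.2 overstates Cohort B combination exposure by the lag between the two first doses: 7 days on schedule, 6 to 8 with the visit window, and more if venetoclax starts later. In relative terms this is 25% at 28 days on both drugs and about 1.1% at 24 cycles. The result rests on study treatment meaning any study drug, which the SAP's other uses support but which it never states.

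The effect is confined to the combination-exposure entries in Tables 14.3.7.5.1 and 14.3.7.5.2. Exposure to each single drug, all Cohort A results, adverse event incidence and ORR are unchanged. Separately, exposure of 7 days or less has no reporting category, although such patients still enter the mean and standard deviation.

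**What to change.** Replace the formula in SAP 4.7.1.2 with: combination exposure (days) = min(last exposure date of MOR00208, last exposure date of idelalisib/venetoclax) − max(first dose date of MOR00208, first dose date of idelalisib/venetoclax) + 1, set to 0 if negative.

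Patients who never received one of the drugs remain missing under 4.14.1; labelling them not applicable would make the table easier to read. A footnote should say that the value is a calendar span, because 4.7.1.1 disregards temporary oral-drug interruptions and the corrected formula does too.

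In SAP 4.7.1.3, change the first category from (1-2] to (0-2] weeks. The definition of a completed oral-drug cycle can stay as it is.

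The cost is a short SAP edit and a small programming change, using dosing dates already collected. Reported Cohort B combination exposure becomes about one week shorter than under the literal formula.
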